### 1) Objectives:

In this project we propose to conduct a 4-week open label cognitive enhancement trial of isradipine in up to 80 stable outpatients with schizophrenia and schizoaffective disorder.

The primary aim of this study is to evaluate the effects of the calcium channel antagonist, isradipine on cognitive dysfunction in patients with schizophrenia and schizoaffective disorder. Incomplete treatment response is common. Cognitive impairment and negative symptoms persist in a majority of patients even when positive psychotic symptoms are well-controlled, and they account for a large proportion of the variance in explaining functional disability (Keefe et al. 2007). This has led to a focused effort to target the specific treatment of cognition in patients with schizophrenia (Green and Nuechterlein, 2004), with somewhat limited success to date.

Novel treatment options have been limited by an incomplete understanding of the biological etiology of schizophrenia; however, recent data from the field of genomics have provided insights into the molecular underpinnings of schizophrenia and its associated symptoms. The majority of genetic risk loci identified to date show trans-disorder effects, increasing susceptibility across a broad range of neuropsychiatric disorders including schizophrenia and bipolar disorder (Williams et al. 2011; Purcell 2009). One possible explanation for this overlap is that several of these genes are influencing risk via their effects on shared phenotypes such as neurocognitive dysfunction. One such example is a single nucleotide polymorphism (SNP; rs1006737) in the calcium channel gene, CACNA1C; initially associated with bipolar illness (Sklar et al. 2008; 2011; Ferreira et al 2008) but also linked with schizophrenia (Green et al. 2009; Nyegaard et al. 2010) and recurrent major depression (Green et al, 2009). The strength of

	Protocol Title:	A Molecular Approach to Treat Cognition in Schizophrenia: Ca 2+ Channel Blockade
	Principal Investigator Name/Contact Info:	[name] [contact]
	Primary Contact Name/Contact Info:	[name] [REDACTED]
	Date Revised:	May 16, 2017
	Study Number:	HSM# 12-0031, GCO# 12-0679, GCO# 13-1987

the association signal for CACNA1C in major mental illness is unambiguous and several subsequent studies have evaluated the effects of CACNA1C variation on neurocognitive capacity.

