### c) Number of Subjects

Up to 80 stable schizophrenia and schizoaffective patients will be recruited from the Mount Sinai Health System Outpatient Departments, and community advertisements.

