### f) Procedures Involved in the Human Research

All eligible subjects will undergo visits at screening, baseline (week 0), visit 8 hours after week 0, week 1, week 2, visit 8 hours after week 2, week 3, and week 4 (end of study). The parameters of study drug dosing are as follows: isradipine as utilized in this trial will be administered twice daily. Isradipine will be titrated as follows: baseline (week 0) 5 mg/day BID; Week 2 increase to 10 mg/day BID if 5 mg was well-tolerated. Dosing will be flexible based on side effects with a maximum=10 mg/day. If 5 mg cannot be tolerated, the subject will be discontinued. Dosing was based on package labeling for hypertension and prior studies in Parkinson's disease (Simuni et al. 2010).

	Protocol Title:	A Molecular Approach to Treat Cognition in Schizophrenia: Ca 2+ Channel Blockade
	Principal Investigator Name/Contact Info:	[name] [contact]
	Primary Contact Name/Contact Info:	[name] [REDACTED]
	Date Revised:	May 16, 2017
	Study Number:	HSM# 12-0031, GCO# 12-0679, GCO# 13-1987

Measures described in detail below:

Safety Outcome Measures

- The Side Effects Checklist (SEC; physician administered) and side effect self-report form – (all visits)
- Vital signs including blood pressure (standing/supine – all visits)
- Blood pressure check within 8 hours of first dose. Staff contact number will be given to subject in case there are any problems before the 8 hour BP check (week 0). An additional blood pressure check 8 hours after increased dosage (week 2).
- Electrocardiogram (ECG); chemistry panel and CBC via blood draw (approximately 2 TSP blood drawn); urinalysis (screening & week 4)
- Urine toxicology (screening)
- Urine pregnancy test for women of childbearing potential (baseline)
- Abnormal Involuntary Movement Scale (AIMS) and Simpson Angus Scale (SAS) (all visits)
- Beck Scale for Suicidal Ideation (SSI) and Columbia Suicide Severity Rating Scale (C-SSRS) (all visits)

Clinical/Symptom Measures

- Structured Clinical Interview for the DSM-IV (SCID-IV) (screening)
- Symptom rating scales including the Brief Psychiatric Rating Scale (BPRS), the Scale for the Assessment of Negative Symptoms (SANS), the Hamilton Rating Scale for Depression (HRSD), the Clinical Global Impression Scale (CGI), the Clinician Administered Rating Scale for Mania (CARS-M) (all visits)

Neurocognitive/Functional Measures

- MATRICS Consensus Cognitive Battery\* (baseline & week 4)

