Data from this study may be used in medical publications or presentations. The information will be de-identified so that individual subjects cannot be recognized and the information will no longer be considered PHI. The information that is collected for research will be analyzed for many years and it is not possible to know how long this analysis and follow-up will take. Therefore, participants are allowing access to this information indefinitely.

Subjects will only be identified with a numerical code in compliance with HIPAA regulations. Raw subject data will be secured in double locked physical control. Digitized raw data will be similarly de-identified using coding and will be secured on an MS SQL server with Windows integrated security.

	Protocol Title:	A Molecular Approach to Treat Cognition in Schizophrenia: Ca 2+ Channel Blockade
	Principal Investigator Name/Contact Info:	[name] [contact]
	Primary Contact Name/Contact Info	[name] [REDACTED]
	Date Revised:	May 16, 2017
	Study Number:	HSM# 12-0031, GCO# 12-0679, GCO# 13-1987

Data analysis plan is included below. All analyses will be based on an intent-to-treat sample of subjects who received at least one dose of isradipine. Since the missing values may be dependent on the observed outcomes, we assume the missing data mechanism to be missing at random, and hence a mixed models analysis will be used to assess the treatment effect of isradipine with fixed effects for week and first order autoregressive covariance structure to evaluate change over time for all of the primary outcome measures. Cognitive measures will be handled differently, as these will only be collected at two time points – if missing data are substantial (or a complete visit is missing), subjects' data will not/cannot be meaningfully analyzed.

*Primary Analyses* will test the following hypotheses based on our specific aims:

To determine the feasibility of 4 weeks of isradipine on cognitive outcomes in SZ.  
Hypothesis: We will successfully recruit up to 80 stable schizophrenia and schizoaffective patients

To determine the safety of 4 weeks of isradipine on cognitive outcomes in SZ.  
Hypothesis: The frequency of new or worsened side effects (clinician-rated; self-reported; lab-based) will not be significantly different from baseline to end of study visit.

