A Fisher exact test will compare time-points by frequencies of new or worsened (compared with baseline) side effect severity ratings – this will be done for all side effects assessed by the SEC.

Differences on laboratory measures (chemistry panel, etc.) will be tested using repeated measures ANCOVA (baseline and week 4) and changes in vital signs (specifically blood pressure) will be assessed using mixed model ANCOVA, to incorporate data at each weekly visit.

Differences on SAS and AIMS total scores will be examined by calculating the  $\tau$ -b rank correlation between score and week for each subject and comparing the distribution of these trend scores with the Conover-Salsburg rank test.

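### The only test named for SAS and AIMS compares groups, but the trial has one open-label arm, so the test cannot show whether scores changed

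*Combined protocol and SAP*

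**What the plan says.** The data analysis plan sits in section 5(h), Data Management and Confidentiality. For SAS and AIMS total scores it has two steps. The first is a tau-b "rank correlation between score and week for each subject". The second is "comparing the distribution of these trend scores with the Conover-Salsburg rank test". It does not say what the distribution is compared with.

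The design has one arm. Section 1 describes a "4-week open label cognitive enhancement trial of isradipine", section 5(c) sets one cohort of up to 80, and section 5(h) bases all analyses on an "intent-to-treat sample of subjects who received at least one dose of isradipine". Section 5(f) schedules both scales at all visits. Nothing in 5(h) covers a subject whose tau-b cannot be computed.

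**The concern.** Once each subject has a tau-b, time has been used up inside that number. What remains is one value per subject, and a between-group rank test then needs at least two sets of subjects. The plan defines only one.

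Safety is one of the aims listed under the primary analyses in 5(h), and this is the only method assigned by name to the two movement scales. If the sentence stands, the analyst must choose a replacement test, and a rule for unchanged scores, without a pre-stated rule and possibly after seeing the data.

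**Working it through.** The plan gives no alpha, power or expected result for this test, so there is no figure to reproduce. The check is whether the test can work with the design as described.

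**Inputs.** N = 80, one group (sections 1, 5(c), 5(h)). One tau-b per subject (5(h)). The plan gives no formula for the test, so the rank score a(R) = (R/(N+1))^p is assumed, with p = 3 or 4.

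**1. Null variance.** For a group of m subjects out of N, the statistic is the sum of a(R) over that group, with null variance

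m(N − m)/(N − 1) × Var(a).

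- As designed, m = 80: 80 × 0/79 × Var(a) = 0, whatever p is. The number of labellings is C(80,80) = 1.
- The statistic is then a constant. With untied scores it is 19.75 for p = 3 and 15.70 for p = 4. The choice of p changes the constant but not the zero variance.
- With a hypothetical 40/40 split, the factor is 40 × 40/79 = 20.25. The variance is 1.57 for p = 3 (SD 1.25), and the SD is 1.17 for p = 4. The missing second group is therefore the cause.

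**2. Ties do not change this.** With p = 4 and 0, 10, 40, 70, 90 or 100% of trend scores tied at zero, the one-group statistic is 15.70, 15.70, 15.07, 12.20, 8.03 or 5.00. (At 100%, every midrank is 40.5, so 80 × (40.5/81)^4 = 80 × 0.0625 = 5.00.) The permutation SD is 0 and p = 1 in every case.

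**3. Direction is invisible.** If all 80 subjects worsen, or all 80 improve, with distinct trend scores, the permutation p is 1 both times. A one-sample signed-rank test on the all-worsen data gives W = 80 × 81/2 = 3240 against a null mean of 1620 and SD √(80 × 81 × 161/24) = 208.5. So z = 1620/208.5 = 7.77 and p = 8 × 10⁻¹⁵. The dataset is deliberately extreme; it shows only that the data can answer the question and the named test cannot.

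**4. Undefined tau-b.** Scores 2, 2, 2, 2, 2 over weeks 0 to 4 give 0/0, as does a single visit. Scores 0, 0, 0, 0, 1 give 4/√(10 × 4) = 0.63. Entry requires an SAS total of at most 6 (section 5(b)), so flat series are plausible, but the documents give no frequency. If 10% to 90% of 80 were flat (an assumption), 8 to 72 subjects would have no trend score.

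**5. Why the rule matters (illustration).** Suppose 75% of the subjects who changed got worse.

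| Constant, of 80 | Changed | Worsened | Worsened among all 80 (exact 95% CI) |
|---|---|---|---|
| 8 | 72 | 54 | 67.5% (56.1–77.6) |
| 40 | 40 | 30 | 37.5% (26.9–49.0) |
| 72 | 8 | 6 | 7.5% (2.8–15.6) |

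Dropping the constant subjects gives 75% in every row. The effect is on the estimate more than on the p-value: with 15 trend scores of +0.45, 5 of −0.45 and 60 zeros, the signed-rank p is 0.025 whether the zeros are dropped or kept by the Pratt method.

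**The case against.** The strongest counter-argument is that SAS and AIMS already have a workable model. Section 5(h) plans a mixed model by week for the primary outcome measures, and then lists safety under the primary analyses. This softens the consequence but does not remove the error, because 5(h) goes on to give these two scales their own, different method.

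A grouping might also be read into the text. Time-points serve as the groups for the Fisher test in 5(h), but here week is already inside each tau-b. Diagnosis or dose reached could define groups, but neither is named. Dose also depends on tolerability under 5(f), and either grouping would ask whether subgroups differ, not whether scores changed.

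It is also fair to say that zero variance with one group is true by definition, that the exponent is assumed, and that the tau-b examples are invented. They show how the problem works and do not predict its size in this trial.

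One further point stands. Keeping tau-b leaves details open:

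- Section 5(f) lists screening and two 8-hour visits, and 5(h) gives none of them a week value. In a constructed case, scores 1, 1, 1, 1, 2 at weeks 0 to 4 give +0.63. Adding a screening score of 3 (coded week −1) and 8-hour scores of 1 turns this into −1/√(26 × 13) = −0.05.
- A subject with only two assessments and any change scores +1 or −1.
- Tau-b ignores the size of a change.

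**Conclusion.** The concern holds. The SAS/AIMS test is wrong as written: in a single cohort with no named comparator or reference value, its null variance is 0 and it carries no information on change. This rests on the test being a between-group rank test and on the absence of any grouping in the plan; it does not depend on the exponent, the ties or the sample size. The missing rule for an undefined tau-b is a secondary gap of unknown size.

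It should be corrected before analysis. The weight is moderate: the scores are still collected and can be analysed, and neither the MCCB endpoint nor patient-by-patient monitoring (section 5(i)) relies on this test.

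**What to change.** Amend the SAS/AIMS sentence in 5(h) before analysis:

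- Keep one tau-b per subject, set it to 0 when the score is constant, and state that this is a convention (no change means no trend).
- Test the trend scores against zero with the one-sample Wilcoxon signed-rank test, using the Pratt method for zeros.
- State that subjects with only one assessment have no trend score, and report their number.
- For each scale, report the numbers worsened, unchanged and improved out of all assessed subjects, with an exact 95% CI for the proportion worsened.
- Say which visits enter the trend, what week value screening and the 8-hour visits take, and how subjects with only two assessments are counted.

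A mixed model by week, as already planned for other measures, is an acceptable alternative if it is named in advance. With no control arm, either analysis describes change during treatment and cannot attribute it to isradipine.

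The core change takes two or three sentences, plus a line on visit coding. No new data are needed.

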### **i) Provisions to Monitor the Data to Ensure the Safety of subjects**

Safety monitoring will be done on a patient by patient basis by the PI and the study physician on weekly visits. Side effects will be monitored closely and all AEs recorded. To increase safety, a blood pressure check will be done within 8 hours of this first dose (baseline). Staff contact number will be given to subject before the first dose in case there are any problems before the 8 hour BP check. Additionally, a blood pressure check will be done within 8 hours of increasing the dosage (week 2).

	Protocol Title:	A Molecular Approach to Treat Cognition in Schizophrenia: Ca 2+ Channel Blockade
	Principal Investigator Name/Contact Info:	[name] [contact]
	Primary Contact Name/Contact Info:	[name] [REDACTED]
	Date Revised:	May 16, 2017
	Study Number:	HSM# 12-0031, GCO# 12-0679, GCO# 13-1987

The PI will summarize all safety related outcomes after each set of 5 patients have completed the study and discuss these results with study physicians. This monitoring will be applied sooner than 5 patients if indicated, or if a SAE or unanticipated event occurs. All SAEs will be reported to the IRB within 24 hours and documented as per protocol. In the case that there are safety concerns from the PI or the IRB, this will be addressed in an ongoing manner. Independent of any SAEs, a Data Safety Monitoring Plan will be submitted to the IRB after the first 15 participants have been enrolled.

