### **j) Withdrawal of Subjects**

If they choose to consent to the study and are eligible to begin the trial, they will be closely monitored and will visit with the study coordinator and study physician. Side effects will be rated weekly at each visit using an adverse events checklist completed by a study physician. Subjects with an exacerbation of psychosis/depression/mania on a 2-point CGI-change score will be discontinued and treated appropriately by the study physician. Suicidal ideation will be assessed at each visit with the Beck (SSI) and the Columbia Suicide Severity Rating Scale (C-SSRS). Significant suicidal ideation will be addressed immediately using the standard clinical response at ISMMS (evaluation at the walk-in clinic/psychiatric emergency room for potential need to hospitalize). Subjects at risk for suicidal behavior will be discontinued. Subjects with any other clinical worsening as noted by study physician, and any instance of an SAE will be discontinued. In addition, subjects who exhibit any inability to follow the protocol will be discontinued and withdrawn from the study.

To ensure orderly termination from the study, the study physician would meet with the subject to discuss termination and discontinuation of medication. Safety measures would be collected and a follow-up visit by phone would be scheduled to further ensure safe discontinuation. Discontinuing isradipine does not require a taper. We will schedule an in-person visit if necessary after the follow-up visit by phone to address any remaining concerns the subject may have.

Subjects may withdraw from the study for any reason at any time by contacting the principal investigator or any of the research staff. It is also possible to withdraw permission for the use and disclosure of any protected information for research, but it must be done in writing to the principal investigator. In the event permission is withdrawn, information that was already collected may still be used if that information is necessary to complete the research study.

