Along with closely monitoring for symptom exacerbation, each visit with the study physician will entail a detailed side effect evaluation, which will include vital signs and a side effect checklist. The most common side effects of isradipine include hypotension, edema, headache, dizziness, palpitations, fatigue, flushing, and constipation. Patients will be educated about the potential for hypotension and its symptoms, and blood pressure and symptoms will be measured at every visit. If the patient develops clinically significant hypotension (e.g., systolic blood pressure equal to or less than 90 mm Hg or diastolic equal to or less than 60 mm Hg, or if they experience significant associated symptoms), or if at any point in the study subsequent to baseline there is a blood pressure drop of 20% or more from blood pressure at baseline, they will be discontinued from the study medication and excluded from the protocol. Rare side effects have also been reported including arrhythmias, syncope, severe hypotension or myocardial infarction. The informed consent process will alert subjects to these potential risks and close monitoring will ensure prompt response to any adverse effects with appropriate treatment and/or study discontinuation, as indicated.

Additional risks are minimal and involve the completion of questionnaires, interviews and paper-pencil/computerized tests. Some of the questions may be distressing to the individual and subjects will be told that they may refuse to answer any questions that they so choose. The testing procedure can sometimes cause fatigue but we will ensure plenty of resting periods during the session and will instruct subjects to notify staff if they would like an additional break. Pain and bruising may be associated with the blood draw for screening labs; however, a trained phlebotomist will perform the procedure to avoid any additional discomfort.

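### SAEs as such, AEs outside the analysed instruments, and discontinuations for AEs enter no planned safety analysis, so the safety hypothesis could be reported as met despite some SAEs

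*Combined protocol and SAP*

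**What the plan says.** Section 5h lists safety among the primary analyses. The hypothesis reads: "The frequency of new or worsened side effects (clinician-rated; self-reported; lab-based) will not be significantly different from baseline to end of study visit".

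The same section gives the analyses that serve it:

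- a Fisher exact test comparing time-points on new or worsened severity ratings, of which it says "this will be done for all side effects assessed by the SEC";
- for laboratory values, "Differences on laboratory measures (chemistry panel, etc.) will be tested using repeated measures ANCOVA (baseline and week 4");
- a mixed-model ANCOVA on vital signs, specifically blood pressure, using the weekly visits;
- a tau-b trend score per subject for the SAS and AIMS totals, compared with the Conover-Salsburg test.

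The analysis set is every subject dosed at least once.

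The events themselves are handled elsewhere. Section 5i states "Side effects will be monitored closely and all AEs recorded", sends SAEs to the IRB within 24 hours, and has the principal investigator summarise safety after every five completers, or sooner after an SAE. Under section 5j, subjects with "any instance of an SAE will be discontinued". That section also says "Side effects will be rated weekly at each visit using an adverse events checklist completed by a study physician", and that safety measures are collected when a subject terminates. Section 6 warns: "Rare side effects have also been reported including arrhythmias, syncope, severe hypotension or myocardial infarction". Section 5f defines the end of study as week 4.

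**The concern.** The protocol treats an SAE as grave enough to end participation, yet neither the safety hypothesis nor any of its tests has a term for one. Overall AE incidence and discontinuation for an AE are also absent. A checklist counts what it lists, at the times it is rated, and the hypothesis looks at a visit that a subject discontinued for an SAE does not attend.

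The conclusion at stake is that four weeks of isradipine is safe in these patients. As written, the criterion is the absence of a significant change between baseline and the end-of-study visit. That could be satisfied while serious events were removing patients before the visit. Section 8 says the results may support larger, pivotal trials. Their planners would want the SAE and AE-discontinuation rates with their uncertainty, and the plan produces neither.

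**Working it through.** **Step 1: look for the events among the planned analyses.** The plan states no alpha, expected AE or SAE rate, or safety-based sample size, so there is no figure to reproduce. The check is a reading of section 5h against sections 5i and 5j.

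| Recorded item | Planned analysis in 5h |
|---|---|
| SEC item ratings | Fisher exact test per item |
| Laboratory values | Repeated measures ANCOVA |
| Blood pressure | Mixed-model ANCOVA |
| SAS and AIMS totals | Trend score and rank test |
| AEs outside these instruments | None |
| Subjects with any AE | None |
| Subjects with an SAE | None |
| Discontinuations for an AE | None |

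**Step 2: what the Fisher test can register.** Assumptions not in the documents: 80 subjects dosed (section 5c says up to 80), two-sided alpha 0.05, and 0/80 with a new or worsened rating at baseline. The test is used as the plan names it. For 0/80 against x/80, the two-sided p is 2 × C(80, x) / C(160, x).

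- x = 3: 2 × (80 × 79 × 78) / (160 × 159 × 158) = 0.245
- x = 4: 0.120
- x = 5: 0.059
- x = 6: 0.028

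Six affected subjects on one item are needed. Three SAEs, all on the same item and all carried into the test, give p = 0.25 if nobody else is affected on that item.

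**Step 3: two readings of the early leavers.** The plan does not choose between them. In both, two subjects without an SAE are affected on the item.

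*Leavers excluded from the end-of-study comparison:*

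| SAE leavers | Affected / remaining | p against 0/80 |
|---|---|---|
| 0 | 2/80 | 0.50 |
| 4 | 2/76 | 0.24 |
| 8 | 2/72 | 0.22 |
| 16 | 2/64 | 0.20 |
| 24 | 2/56 | 0.17 |

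The number needed for significance falls a little (5 of 76, 4 of 72), but the SAE subjects cannot contribute to it.

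*Exit ratings carried in:* four SAEs on that item plus the two others make 6/80, p = 0.028. The item becomes significant.

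So the answer depends on a rule that the plan does not give.

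**Step 4: what a direct report would show.** Exact (Clopper-Pearson) 95% intervals for the proportion of dosed subjects with an SAE:

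- 0/80: upper limit 1 − 0.025^(1/80) = 4.5%
- 3/80 = 3.8%: 0.8% to 10.6%
- 4/80 = 5%: 1.4% to 12.3%
- 0/40: upper limit 1 − 0.025^(1/40) = 8.8%
- 4/40 = 10%: 2.8% to 23.7%

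**The case against.** A reader might infer that no AE or SAE reaches any planned analysis, and that the safety hypothesis can be met whatever the SAE count. The documents support neither.

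- The adverse events checklist in section 5j is probably the physician-administered SEC of section 5f. That is an inference, but the natural one. If so, AEs that match SEC items are tested. AEs that appear as laboratory, blood-pressure or SAS/AIMS changes are analysed in any case.
- Stopping treatment does not remove a subject from the analysis set, and section 5j collects safety measures at termination. If those ratings enter the Fisher test, SAEs concentrated on one item can make it significant, as step 3 shows.
- The SEC's items are not in the documents, so nobody can say from them which serious events it would miss.
- The five-completer summary and the IRB reports do cover SAEs, and a Data Safety Monitoring Plan goes to the IRB after 15 participants are enrolled. That plan is not available here.
- Sections 1 and 5e make cognition the primary aim and endpoint. This is not solely a safety trial, although section 5h does place safety under its primary analyses.

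These points remove the absolute claims. They do not fill the gap. The summary and the IRB reports are monitoring: they are given no statistic or denominator and do not feed the hypothesis. Even on the reading most favourable to the plan, SAEs are not counted as SAEs, and neither off-instrument AEs nor AE-led discontinuations are counted at all.

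**Conclusion.** The concern holds in a limited form. SAEs as such, AEs outside the SEC, laboratory, blood-pressure and SAS/AIMS measures, and discontinuations for AEs have no planned analysis, although the protocol records all AEs and ends participation for any SAE. The hypothesis could be reported as met despite SAEs that are not on the SEC or not carried into the test.

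The reading of section 5h needs no assumption. The size does: with 80 dosed, alpha 0.05 and a clean baseline, an item with five or fewer affected subjects does not reach significance. The SAE counts used are illustrations, since the documents give no expected rate. Zero SAEs would exclude only rates above 4.5% with 80 dosed, or above 8.8% with 40, and the plan would not report that bound. This goes beyond missing detail, because it concerns what the safety conclusion rests on.

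**What to change.** In section 5h, for all subjects who received at least one dose, report the number and percentage with:

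1. at least one AE;
2. at least one SAE;
3. at least one AE that led to discontinuation of isradipine.

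Give each with an exact 95% CI. State that the safety conclusion rests on these results together with the SEC, laboratory, blood-pressure and SAS/AIMS results, so that a set of non-significant tests does not settle it alone. State also that safety measures collected at early termination enter the SEC comparison.

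A breakdown by dose at onset should be added only if the AE record captures it, which the protocol does not say.

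The analysis set is already defined in section 5h and AE recording is already required by section 5i. The change adds one table and a short paragraph, and alters no visit, dose or clinical rule. The downside is that the safety statement may read slightly less favourably.

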## **h) Data Management and Confidentiality**

If a participant agrees to be in this study, we will collect health information that identifies them, “Protected Health Information” (PHI). We may collect the results of tests, questionnaires and interviews. We may collect information from a patient’s medical record. We will only collect information that is needed for the research. This information is described in the consent form. By signing the consent form a participant gives us permission (authorization) to collect, use and share their health information.

Data collected will include questionnaires and assessments as described above in section (5f). Labs and tests will be done at the ISMMS laboratory and information sent to the PI, data for these will be stored in a binder which will be secured in a double locked fashion. Blood samples will be labeled with de-identified codes, which cannot be associated with individual subjects. PHI, such as patient name and DOB, will only be included in a separate file including the consent documents. All other data collected for the study will be de-identified and stored apart from PHI, identified by study number linked to PHI in a secure file. This data will be stored indefinitely.

The PI will be responsible for receipt and transmission of study data and specimens. Quality control of the data collected will include double data entry and data quality check by investigators after each 5 subjects completed.

Study staff will have access to data and records may be reviewed by the Mount Sinai School of Medicine Institutional Review or government agencies (i.e. NIH) in order to meet federal or state research regulations. Please be aware that once private information is disclosed, it is subject to re-disclosure by the recipient and can no longer be considered protected. If research records are used for decisions related to clinical care, then a participant has the right to review this information and to request changes. This is limited to information about their treatment, and does not include information related to procedures or tests that are for research purposes only. Participants may access this information only after the study analysis is complete.

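### Section 5i times its scheduled safety reviews by completers, so early removals for toxicity slow them, and the monitoring plan is due only after 15 patients are enrolled

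*Combined protocol and SAP*

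**What the plan says.** Section 5i provides weekly patient-by-patient monitoring and blood pressure checks within 8 hours of the first dose and of the week-2 increase. On top of that it sets a scheduled summary: "The PI will summarize all safety related outcomes after each set of 5 patients have completed the study and discuss these results with study physicians". There is an earlier trigger: "This monitoring will be applied sooner than 5 patients if indicated, or if a SAE or unanticipated event occurs". The IRB is informed directly: "All SAEs will be reported to the IRB within 24 hours and documented as per protocol". The response to a concern is left general: "In the case that there are safety concerns from the PI or the IRB, this will be addressed in an ongoing manner". Finally, "a Data Safety Monitoring Plan will be submitted to the IRB after the first 15 participants have been enrolled".

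Three other places bear on the count:

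- Section 5h uses the same kind of count for data quality: "data quality check by investigators after each 5 subjects completed".
- Section 5h defines the analysis set by dosing: "All analyses will be based on an intent-to-treat sample of subjects who received at least one dose of isradipine".
- Section 5j, on orderly termination, says "Safety measures would be collected". Safety data on patients who leave early are therefore already to be collected.

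The limits for removing an individual patient are in Section 5f (5 mg not tolerated), Section 5j (CGI worsening, suicide risk, any SAE) and Section 6 (clear symptom worsening, blood pressure).

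**The concern.** Removals are foreseeable here. Section 5b excludes patients on treatment for hypertension, Section 5f gives them an antihypertensive with an increase at week 2, and Section 6 lists hypotension among the common side effects and removes a patient for a 20% fall in blood pressure alone. If only completers move the review count, a higher rate of such removals makes the scheduled review later and less frequent, which is the wrong direction for a safety schedule. A non-serious hypotension removal brings a review forward only if someone judges it indicated or regards the event as unanticipated.

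The monitoring plan's due date adds to this, because the first 15 patients can be enrolled before that document reaches the IRB. Safety is one of the stated aims in Section 5h.

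**Working it through.** The documents give no removal rate and no figure to reproduce, so the removal rate p is an assumption, shown at 10%, 20%, 30% and 40%.

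**Inputs from the documents.** Maximum of 80 patients (Section 5c); about 24 months of enrolment, taken as 104 weeks (Section 5d); 4 weeks on drug (Section 5d); a review per 5 completed and a plan after 15 enrolled (Section 5i).

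**Step 1: dosed patients per scheduled review.** If only completers count, the mean number dosed per review is 5/(1 − p). The number of scheduled reviews over 80 dosed patients is about 80(1 − p)/5, against 80/5 = 16 if everyone dosed counts.

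| p | 5/(1 − p) | 80(1 − p)/5 |
|---|---|---|
| 10% | 5.6 | 14.4 |
| 20% | 6.3 | 12.8 |
| 30% | 7.1 | 11.2 |
| 40% | 8.3 | 9.6 |

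**Step 2: where the count stands at the 15th enrolment.** Accrual is 80/104 = 0.77 per week, so about 4 × 0.77 = 3.1 of the 14 earlier patients are still within their 4 weeks, and about 14 − 3.1 = 10.9 are past them. Expected completers are 10.9(1 − p) = 9.8, 8.7, 7.6 and 6.5. On average the first review has come due at every rate. The question is how often it has not.

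**Step 3: chance that no scheduled review has come due by the 15th enrolment.** This was simulated with the first patient dosed at time 0, Poisson accrual, completion at week 4 and removals spread uniformly over the 4 weeks.

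| p | Completers only, 80 patients | Completers only, 40 patients |
|---|---|---|
| 10% | 0.005 | below 0.001 |
| 20% | 0.016 | 0.002 |
| 30% | 0.054 | 0.012 |
| 40% | 0.141 | 0.055 |

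If early removals also count, the figure for 80 patients is about 0.001 or less at each of these rates. Repeat runs for 80 patients differ by a few units in the third decimal. The 40-patient column assumes slower accrual over the same 24 months. With 80 patients, counting completers delays the first review by a mean of 0.9, 2.0, 3.4 or 5.2 weeks relative to counting everyone who has finished or left.

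**Step 4: timing of the plan.** 15/80 = 19% of the maximum. With even accrual, 15/(80/24) = 4.5 months.

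**The case against.** The strongest reply is that a run of toxicity removals is exactly what the earlier-if-indicated trigger is for. The trial is open label and single-site, the investigator and study physician follow each patient weekly, and the IRB hears of every SAE within 24 hours. The people who would hold the review see each removal as it happens. This stands, and it limits the point to the scheduled reviews. The probabilities above leave out all unscheduled ones.

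Second, completing the study might mean finishing participation by any route. That is possible, although Section 5j treats discontinued patients separately, so completers is the more natural reading. If the looser meaning is intended, the first change is a clarification.

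Third, the choice of benchmark matters. The chance of fewer than two scheduled reviews by the 15th enrolment is 0.41, 0.64, 0.83 or 0.94 with 80 patients. Those figures look alarming, but nothing in the documents makes two reviews a standard, and the chance is already about 0.20 with no removals at all. The chance of no review is the fairer measure.

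A reader might also infer three stronger criticisms that the documents do not support:

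- **That the lack of a trial-level rule for pausing enrolment is itself a defect.** No such rule is written. Given the individual limits, the 24-hour reporting and the unscheduled reviews, leaving a pause to the investigator and the IRB is a choice on which reasonable reviewers differ. A pause triggered by related SAEs would also miss non-serious hypotension and would need a relatedness judgement that the protocol does not describe.
- **That removed patients are left out of the safety summary.** Section 5i has the summary cover all safety outcomes. Only its timing is tied to completers.
- **That Section 5i contradicts the analysis set in Section 5h.** One sets when a summary is made, the other who is analysed.

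**Conclusion.** The point holds as a modest weakness in timing, worth considering for change. The scheduled review slows as early removals rise, and the monitoring plan arrives after the first 15 enrolments. At assumed removal rates up to 20% the practical effect is slight: the chance of no scheduled review by the 15th enrolment is about 0.02 or less. At 40% it is about 0.14. These figures rest on the completer reading, on assumed removal rates, and on 80 patients accrued evenly over 24 months. Slower accrual makes them smaller.

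This is not an absence of oversight, and no number of avoidable events can be claimed. The contents of the monitoring plan are not in the documents, so nothing is concluded about what it would add. The version is dated May 2017 with an anticipated end in 7/2017. The documents do not say whether the 15-patient mark has passed or the plan has been submitted.

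**What to change.** Make two changes in Section 5i.

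1. Hold the scheduled review each time 5 further dosed patients have either completed week 4 or left early. Keep the existing earlier triggers unchanged.
2. Submit the Data Safety Monitoring Plan before the first dose. If enrolment has begun and the plan has not yet been submitted, submit it before any further patient is dosed.

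The cost is somewhat more frequent summaries and an earlier date for a document already promised. No new data are needed, because Section 5j already has safety measures collected at early termination. The benefit is small if few patients remain to be dosed. Whether to add a trial-level pause rule is an optional matter for the clinicians and the IRB.
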